3. OBJECTIVES

3.1 Primary objective

The study will compare the level of thermal care delivered to a clinically stable baby in the mOm incubator and a standard (non-humidified) incubator.

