8. STATISTICS AND DATA ANALYSIS

The primary endpoint is babies' truncal skin surface temperature variation; also termed core or central temperature. This is expected to fluctuate but remain within normal temperature limits (36.5 to 37.5 degrees Celsius). Variations from this endpoint will be analysed and compared statistically between the two arms of the study.

Thirty-six completed datasets are required for the analysis to be valid. A complete subject dataset will be deemed acceptable if 19 of the 24, once-hourly temperature observations have been recorded for each incubator type (*i.e.* 79% compliance). This degree of compliance was considered acceptable for analysis because it is still greater than the routine standard for this type of incubator care for clinically stable infants of 30 weeks GA or greater, which is often every three hours. Although data analysis will be largely descriptive, the performance of the mOm incubator will be statistically quantified by assessment of the fluctuations of babies' temperatures during each 24-hour period. It is expected that these babies' temperatures will fluctuate by around one degree Celsius, and this is normal. Thus, analysis will explore whether fluctuations for each baby keep within this bound. A 95% confidence interval will be calculated around the mean of these fluctuations within each baby for each of the two incubators. Data from 36 babies would allow such a confidence interval to be calculated to within plus or minus 0.33 of a degree if the actual mean fluctuations are around one degree (*i.e.* as normally expected) and assuming a two-sided confidence interval.

Each patient will serve as their own control. The order of incubator type used for each of the two consecutive 24-hour periods of incubator care, and therefore which study arm the subject is recruited to, will be assigned randomly. A Microsoft Excel random number generation system will be used to generate random numbers with which the arm of the study which the subject is to enter will be assigned. Each assignment will be placed in an envelope attached to each CRF already numbered with a continuous series subject number.

Baseline demographic factors of the study subjects will be summarised. For continuous variables, such as weight, the mean, standard deviation, median and range will be presented. For categorical variables, such as gender, the proportion of subjects in each category will be presented.

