All data will be analysed based on intention-to-treat. Statistical analysis will focus on babies' temperature fluctuations whilst in each of the two incubators. Graphical displays of these, as well as summary statistics such as the variance of temperature throughout the two 24-hour periods will be presented. A 95% confidence interval for the size of these temperature fluctuations for each incubator type will be calculated and this measure will be used to consider whether the mOm incubator works as well as the standard one in maintaining temperature control. Secondary outcome measures will be presented similarly.

Questionnaire data will be summarised to assess usability and acceptability of the mOm incubator to the clinical research team (staff).

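### The ±0.33 °C behind the 36 babies rests on an unstated between-baby SD, not on the mean, and no precision is given for the within-baby mOm–standard difference

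*Combined protocol and SAP*

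**What the plan says.** The primary objective (Section 3.1) is to "compare the level of thermal care delivered to a clinically stable baby in the mOm incubator and a standard (non-humidified) incubator", and Section 2 sets out an as-good-as hypothesis.

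Section 8 then makes these statements:

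- On estimation: "A 95% confidence interval will be calculated around the mean of these fluctuations within each baby for each of the two incubators". With 36 babies, the two-sided interval is said to reach "plus or minus 0.33 of a degree if the actual mean fluctuations are around one degree". No other justification for 36 is given, and no SD appears.
- On a benchmark: a swing of about one degree is called normal, and the analysis is to look at whether each baby stays within it.
- On comparison: "Variations from this endpoint will be analysed and compared statistically between the two arms of the study", and "Each patient will serve as their own control".
- On the conclusion: a 95% interval is calculated for each incubator type, and "this measure will be used to consider whether the mOm incubator works as well as the standard one in maintaining temperature control".
- On the measure: "summary statistics such as the variance of temperature throughout the two 24-hour periods will be presented". Whether a baby's fluctuation is a range, an SD or a variance is not defined.
- On order: "A Microsoft Excel random number generation system will be used to generate random numbers" that assign the sequence. No balancing of the two orders is described.

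**The concern.** There are two linked problems.

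First, the condition attached to ±0.33 is the wrong quantity. The width of a confidence interval for a mean is set by the spread between babies and the number of babies. The size of the mean does not enter. As written, the only support for 36 does not follow from its stated condition, and a reader cannot judge whether the SD behind it is reasonable.

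Second, the figure is for one incubator's mean. The trial is a cross-over with a comparative objective, so the quantity of interest is the within-baby difference. The measure Section 8 names for judging whether mOm does as well is the interval for each incubator type, which does not use the pairing. A comparison is promised, but its method is not stated and its precision is not given. At stake is how sharply the trial can answer its main question, which the plan at present does not tell the reader.

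**Working it through.** **Inputs from Section 8.** n = 36 babies, each in both incubators; two-sided 95% interval; stated half-width 0.33 °C; mean fluctuation about 1 °C. **Not in the documents:** the between-baby SD of the fluctuation and the within-baby correlation (rho) between incubators. All values of these below are assumptions. The figures apply only if fluctuation is one value per baby per incubator, in °C.

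**Step 1: reproduce ±0.33.** Half-width = 1.96 × SD/√n.

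- With SD = 1.0: 1.96 × 1.0/6 = 0.327, which rounds to 0.33.
- Solving for n: (1.96/0.33)² = 35.3, so 36.
- Solving for the SD: 0.33 × 6/1.96 = 1.01 °C.

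The figure is therefore the normal-based (z) half-width for one mean with an SD of about 1 °C. With the t distribution (35 df, 2.030) it would be 2.030 × 1.0/6 = 0.338.

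**Step 2: hold the mean at one degree and vary the SD (z).**

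- SD 0.5: 1.96 × 0.5/6 = 0.163, so ±0.16.
- SD 0.3: 1.96 × 0.3/6 = 0.098, so ±0.10.
- SD 1.5: 1.96 × 1.5/6 = 0.490, so ±0.49.

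The stated condition is met in all three cases, and the stated precision in none of them.

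**Step 3: precision of the mOm-minus-standard difference.** Take the equally weighted average of the two sequence-group mean differences, which removes a period effect. With equal SDs in the two incubators, SD_diff = SD × √(2(1 − rho)), and half-width = t(34) × SD_diff × 0.5 × √(1/n1 + 1/n2), with t(34) = 2.032. For 18:18 this reduces to 2.032 × SD_diff/6.

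| SD (°C) | rho 0 | rho 0.5 | rho 0.8 |
|---|---|---|---|
| 1.0 | ±0.48 | ±0.34 | ±0.21 |
| 0.5 | ±0.24 | ±0.17 | ±0.11 |

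For example, at SD 1.0 and rho 0: SD_diff = 1.414, and 2.032 × 1.414/6 = 0.479. On the same t basis, the single-incubator half-width at SD 1.0 is 0.34. So the difference is estimated about as precisely as one incubator's mean at rho 0.5, less precisely below that and more precisely above it.

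**The case against.** Four points on the other side deserve weight.

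- **The per-incubator interval has a use.** Section 8 treats about one degree as a bound, and each incubator can be read against it. For that purpose a single-incubator half-width is the right precision. This stands, and the intervals should stay. It does not cover the comparative objective.
- **A paired comparison is already promised.** Section 8 says that the arms will be compared statistically and that each baby is its own control. This also stands. A reader might infer that the trial's conclusion can only rest on two unpaired intervals; the documents do not support that. The narrower point is that the method of comparison is unspecified while a different measure is named for the conclusion. Nor do the documents say that the two intervals will be read by whether they overlap, so no argument here depends on that.
- **The analysis is described as largely descriptive, and the multiplication is right.** Both are true. Even so, a precision figure that supports the sample size should name the quantity it depends on, and a descriptive cross-over can still report its within-baby difference.
- **Random order already protects the comparison.** Randomisation leaves the unadjusted difference unbiased on average, and no period effect is documented. Period adjustment is therefore a sensible safeguard where no balance of order is stated, not a necessity.

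**Conclusion.** The point holds in this form. The ±0.33 °C is conditioned on a mean when it depends on a between-baby SD of about 1 °C that is neither stated nor given a basis. No precision is given for the within-baby difference that the objective and design call for. Under the assumed SDs of 0.5 and 1.0 °C and correlations of 0 to 0.8, that precision lies between ±0.11 and ±0.48 °C, and the documents do not allow a choice within that range.

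A reader might go on to infer that 36 babies are too few. The documents do not support this. An SD as large as the mean is wide for a quantity that cannot be negative, such as a range, and the normal band in Section 8 is only 1 °C across (36.5 to 37.5). The true SD may well be smaller and ±0.33 conservative. The formula point is certain; the tabulated sizes are only as good as the assumed SDs and correlations and the assumed °C scale. The point sets no margin for doing as well, because the documents give no basis for one.

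**What to change.** Keep 36 babies and amend Section 8.

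1. **Precision statement.** Replace the condition on the mean with: *if the between-baby SD of the fluctuation is 1.0 °C (assumed)*, with the sponsor giving the basis for that value. Add that the half-width scales with the SD: about ±0.16 at 0.5 °C and ±0.10 at 0.3 °C (z). Define the fluctuation as one value per baby per incubator in °C. This is needed because the variance, which Section 8 also names, is in °C squared.
2. **Comparison.** Keep the per-incubator intervals for description and for the one-degree bound. State that the comparison will be judged from *the 95% confidence interval for the mean within-baby difference (mOm minus standard), adjusted for period as the equally weighted average of the two sequence-group mean differences*.
3. **Precision of the difference.** Give it as a range, not as a single planning value: with 18:18 sequences and t(34), ±0.48 / 0.34 / 0.21 at SD 1.0 and ±0.24 / 0.17 / 0.11 at SD 0.5, for rho 0 / 0.5 / 0.8, all labelled as assumed.

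The cost is a few clauses of text and one adjusted analysis, with no extra babies, visits or data. The downside is that the stated precision for the comparison may look less favourable than ±0.33, for example ±0.48 at SD 1.0 and rho 0.

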4.2.2 Temperature stability and regulation	11
4.2.3 Usability	11
4.2.4 Adverse events	11
4.2.5 Staff feedback	11
5. STUDY DESIGN	11
6. STUDY PROCEDURES	12
6.1 Recruitment	12
6.2 Procedure	13

6.3 Inclusion / Exclusion Criteria	14
6.3.1 Inclusion criteria	14
6.3.2 Exclusion criteria	14
6.4 Withdrawal of Patients from the study	14
7. ADVERSE EVENTS	15
7.1 Adverse event (AE)	15
7.2 Anticipated Adverse Event	15
7.3 Serious Adverse Events	15
7.4 Reporting of Adverse Events	15
8. STATISTICS AND DATA ANALYSIS	19
9. ETHICS	20
9.1 Declaration of Helsinki	20
9.2 Independent Ethics Committee Approval	20
9.3 Informed Consent	20
10. SUBJECT CONFIDENTIALITY	20
11. DATA MANAGEMENT	20
11.1 Data Quality Assurance	21
11.2 Data Storage at the end of the study	21
12. FINANCING AND INSURANCE/INDEMNITY	22
13. CLINICAL SUPPLIES	22
14. REPORTING AND DISSEMINATION OF STUDY OUTCOMES	22
15. REFERENCES	22
16. INVESTIGATOR APPROVAL STATEMENT	24

ii. KEY STUDY CONTACTS

Chief Investigator (CI) and Medical Expert	[name], Neonatology Consultant, Ashford and St Peter's Hospitals NHS Foundation Trust, St Peter's Hospital, [name] [contact] [name]
Study Co-ordinator (Project manager)	[name], Director of Clinical Affairs, mOm Incubators Limited [contact] [name]
Sponsor	mOm Incubators Limited, [name] www.mominubators.com
Funder	Sponsor funded: mOm Incubators Limited
Key Protocol Contributors	[name] and mOm Incubators Limited

iii. CLINICAL INVESTIGATION PLAN AMENDMENT HISTORY

Amendment No.	CIP Version No.	Date issued	Author(s) of changes	Details of Changes made
N/a	1.0	10 April 2018	[name], [name] (statistician) and [name]	Original Clinical Investigation Plan
1	2.0	23 July 2021	[name]	Title Updated Dates and staff role/details updated. Adverse event causality updated to MDR/MDCG guidance requirements.
2	3.0	09 March 2022	[name]	Updated to clarify when recordings are required for each

				clinical data parameter and updated target recruitment period.
--	--	--	--	--

iv. STUDY SUMMARY

Study Title	Comparison of the mOm incubator with a standard incubator for the maintenance of thermal stability in infants ($\leq 6\text{kg}$)
Internal ref.	mOm/2018/01
Study Design	Prospective, multi-centred, randomised, controlled, cross-over study

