5. STUDY DESIGN

The study has a prospective, multi-centre, randomised controlled, cross-over design. There will be two arms to the research. The first arm will consist of mOm incubator

care for 24 hours, followed by a further 24 hours where the subject is transferred for care to a standard incubator. The second arm will consist of 24 hours care in a standard incubator followed by 24 hours care in a mOm incubator. The care of the baby (subject) is mostly unchanged from standard incubator care, but observations may be recorded more frequently (*i.e.* hourly) for incubator displayed temperatures and some other physiological measures of clinical stability than would normally be collected in routine care for this type of clinically stable baby of at least 30 weeks GA (normally every three hours) (See Table 1). No additional blood tests or any other invasive testing or monitoring are required. The clinical research team will have full control and responsibility for the baby's care, with the ability to withdraw the baby from the study at any time for any reason if they feel the baby is clinically unstable or is adversely affected by their environment. The order of incubator type in which the baby is cared for (*i.e.* which arm of the study) before being crossed over to the alternative incubator type will be assigned at random at the point of written consent being gained and the subject therefore having been officially recruited.

Babies that are considered clinically stable from a cardio-respiratory point of view but require at least 48 hours incubator care but not requiring additional humidification will be recruited to the study from the Neonatal Unit. In practice, this will mostly be babies weighing less than approximately 1400g at 30 weeks, although some term babies may also be eligible for the study if they are being nursed in an incubator for clinical reasons.

The aim is to collect 36 completed data sets for analysis; to achieve this approximately 40 babies will be recruited; recruitment will be stopped once 36 completed data sets are available. The target is to complete recruitment within a nine-month period.

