6.2 Procedure

There will be two arms to the protocol as detailed in section 5. The Case Report Form labelled with the appropriate subject number contains the data forms for that subject and a randomisation envelope attached inside the cover of the CRF which indicates which incubator type (standard or mOm) will be used for the baby to spend the first 24 hours in, before being switched to the alternate incubator type for a further 24 hours.

All data collected for the duration of the study will be entered in the appropriate source data (e.g. medical notes, electronic data capture systems, cleaning logs etc) and into the subject's CRF. Adverse events (AE) should be entered.

Baseline data such as length, weight, gender, core/truncal temperature (recorded at time point 0 in physiological recordings section), GA at birth, date of birth and current age of the baby will be recorded on entry to the study. Hourly observations (+/- 15 minutes) will be taken throughout the following 48 hours of incubator care, and will include temperature data displayed on the incubator, plus routine clinical observations of the baby (i.e. pulse rate, O₂ saturation and respiration rate), plus axillary temperature as per standard practice and blood pressure recorded at least once per day (See Table 1 below)

Table 1: Clinical Data Recording

Parameter	Frequency
Core/Truncal Temperature	Hourly
Pulse Rate	Hourly
Oxygen Saturation	Hourly
Respiration Rate	Hourly
Axillary Temperature	As per standard of care (usually every 2-4hrs)
Blood Pressure	As per standard of care (at least once per day)
Events (e.g. door open for feeding, care, baby removed for cuddles)	For each event record start and end time, type of activity, number of portholes/door open, any error/alarms on the incubators and any comments.

Each incubator will be individually identified by serial number for reference in CRFs, source documents (medical record/chart) and on cleaning logs. The randomisation details and the identification number of the incubators used will be recorded when the subject put into the first incubator; likewise, at the 24 hours cross-over point.

Further details about the mOm incubator can be found in the Investigator brochure (IB) filed in the ISF. For the incubator, hourly temperature readings from the digital display, time to set up, time to clean, types of cleaning performed and reasons/times when incubator opened to administer to baby's care will be recorded.

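### Incubator order is assigned by Excel random numbers with no stated restriction, and the planned analysis has no period term to correct for an unequal split

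*Combined protocol and SAP*

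**What the plan says.** The Study Summary gives the design as "Prospective, multi-centred, randomised, controlled, cross-over study". The number of sites is not given.

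- **Generating the order.** Section 8: "A Microsoft Excel random number generation system will be used to generate random numbers". No block, fixed total per order or stratification by site is described there or elsewhere.
- **Holding the assignment.** Section 6.2 refers to "a randomisation envelope attached inside the cover of the CRF". Section 8 adds that the CRFs are numbered beforehand in one running series. Sealing, opacity, custody and a record of opening are not mentioned.
- **Timing.** Section 5 places the random assignment at written consent, and Section 6.1 issues the subject number after consent.
- **Size.** Section 8: "Thirty-six completed datasets are required for the analysis to be valid". Section 5: "to achieve this approximately 40 babies will be recruited", and "recruitment will be stopped once 36 completed data sets are available". There is no rule on completers per order.
- **Analysis.** Section 8: "A 95% confidence interval for the size of these temperature fluctuations for each incubator type will be calculated". That measure is to be the basis for judging whether mOm works as well as the standard incubator. The section says each baby is its own control, but it names no paired-difference analysis and no period, sequence or site term.
- **Precision.** Section 8: "Data from 36 babies would allow such a confidence interval to be calculated to within plus or minus 0.33 of a degree".

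**The concern.** In a two-period cross-over, anything that changes between the first and second 24 hours, such as maturation or settling, affects the two incubators equally only if the two orders have equal numbers. If the orders are unequal, part of that change appears as a difference between incubators. Using each baby as its own control removes differences between babies. It does not remove a shift from day 1 to day 2.

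There are two usual protections: restrict the randomisation so the orders come out nearly equal, or fit a period term so that the split does not matter. The plan describes neither. What is at stake is a small avoidable distortion in the one comparison the trial is built to make.

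A smaller, related gap is concealment. The plan's timing rule is sound, but no described mechanism enforces it.

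**Working it through.** **Inputs.** From the documents: 36 completers, about 40 recruited, two orders, two-sided 95% intervals, half-width 0.33 °C. Assumed, because the documents are silent: simple 1:1 randomisation; completion unrelated to order; an SD of 1.0 °C (Section 8 gives a mean fluctuation of about one degree, not an SD); a period effect π (day 2 minus day 1) of 0.1 to 0.5 °C.

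**1. The plan's own figures.** Half-width = 1.960 × 1.0 / √36 = 0.327, which rounds to 0.33. With t on 35 degrees of freedom it is 0.338. Solving back, the SD implied by 0.33 is 1.01 (normal) or 0.98 (t). Recruitment: 36 / 0.90 = 40, an implied 10% non-completion. Both figures reproduce, and neither depends on the order split.

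**2. Chance of an unequal split.** With X ~ Binomial(36, 0.5), the chance of exactly 18:18 is 0.13. The chance of a given split or worse is 2 P(X ≥ larger group), shown in the table.

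**3. Leakage into the difference.** Let τ be the true mOm-minus-standard difference. A baby who has mOm first contributes τ − π on average, and a baby who has standard first contributes τ + π. With n1 babies having standard first and n2 having mOm first, the unadjusted mean difference is τ + π(n1 − n2)/36. Each incubator's own mean moves by half of that: π(n1 − n2)/72.

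**4. Cost of a period term.** The period-adjusted estimate is the average of the mean differences in the two orders. π then cancels at any split. Its standard error, relative to the unadjusted mean, is √[36² / (4 n1 n2)].

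- At 22:14: √(1296 / 1232) = 1.026.
- At 24:12: √(1296 / 1152) = 1.061.

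| Split | Chance of this or worse | Share of π in the difference | Leakage, π = 0.1 | π = 0.2 | π = 0.5 | SE rise with period term |
|---|---|---|---|---|---|---|
| 22:14 | 24.3% | 8/36 = 0.22 | 0.022 °C | 0.044 °C | 0.111 °C | 2.6% |
| 24:12 | 6.5% | 12/36 = 0.33 | 0.033 °C | 0.067 °C | 0.167 °C | 6.1% |

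The shift in each incubator's mean is half the leakage: 0.011 to 0.056 °C at 22:14 and 0.017 to 0.083 °C at 24:12. These halved figures are the like-for-like comparison with 0.33 °C, because the plan's half-width is for one incubator. The half-width of a paired difference would need a within-baby SD, which the documents do not give.

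**The case against.** The case for leaving the plan alone is fair in several respects.

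- **The effect is small and has no preferred direction.** Averaged over randomisations the bias is zero. Every baby uses both incubators, so only a fraction of any period effect leaks through. This stands, and it limits the weight of the point. The trial will, however, have one realised split, and the planned analysis would not correct for it.
- **Silence is not proof of simple randomisation.** Excel can produce a blocked list as easily as an unblocked one. This also stands: the imbalance figures are conditional on the list being unrestricted, and the plan should say whether it is.
- **Blocking alone is not the answer.** It balances recruits, but recruitment stops at 36 completers with no rule per order, so 18:18 is not assured. This is correct, and it is why the period term is the more important half of the fix.

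A reader might infer stronger things that the documents do not support:

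- *That order is known before consent.* Sections 5 and 6.1 place the assignment and the subject number at or after consent. The gap is only that no sealing, custody or opening record backs this up, while the envelope sits in a consecutively numbered CRF.
- *That the person judging eligibility holds the unused CRFs.* No section says who holds them.
- *That foreknowledge would give the two devices different babies.* It could not among completers, since each is nursed in both.
- *That uneven splits at individual sites add bias.* With a common period effect, only the overall split matters for the overall comparison.

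**Conclusion.** The point holds as a modest improvement. As written, the plan states no restriction on the order list and no analysis that would absorb an unequal split. If the list is simple randomisation, there is about a one-in-four chance of 22:14 or worse and a 6.5% chance of 24:12 or worse. Across those two splits the mOm-minus-standard difference would carry 0.22 to 0.33 of any day-1-to-day-2 change, or about 0.02 to 0.17 °C over the assumed range of period effects.

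This rests on three assumptions: unrestricted assignment, completion unrelated to order, and a period effect that is the same in both orders. The size of that period effect is not documented. The calculation does not address carry-over, and a period term would not remove it. The sample size of 36 and the stated precision are unaffected. Nothing here suggests that the trial would reach a wrong conclusion on this account alone.

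**What to change.** 1. **Section 8, order list.** State that the list is generated in permuted blocks of varying size; the same Excel tool will do. Stratification by site is optional. If it is used, the single running series of CRF numbers has to be divided between sites.
2. **Section 8, analysis.** Make the comparison the within-baby mOm-minus-standard difference, with a period term and a 95% confidence interval, and keep the per-incubator intervals as description. This removes the leakage at any completer split, for the small rise in standard error shown above. It can be adopted even if the list already exists.
3. **Section 6.2, envelopes.** Use sealed, opaque, numbered envelopes kept apart from the CRF. Open each one only after consent, eligibility and baseline have been recorded.

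The cost is a new list and a few sentences in Sections 6.2 and 8, with no extra babies. There are two small downsides. Someone must have custody of the envelopes. In an unblinded trial, blocks also make some later assignments easier to guess, which varying the block size limits but does not abolish.

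### The comparative conclusion is to be read from a separate confidence interval for each incubator; no within-baby difference (mOm minus standard) is specified

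*Combined protocol and SAP*

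**What the plan says.** Section 2 (Rationale) states a comparative hypothesis and gives direct comparison as the reason for the cross-over. Section 8 (Statistics and Data Analysis) adds: "Each patient will serve as their own control".

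For the analysis, section 8 says "A 95% confidence interval for the size of these temperature fluctuations for each incubator type will be calculated", and then that "this measure will be used to consider whether the mOm incubator works as well as the standard one in maintaining temperature control". The sample-size paragraph describes the same interval for each incubator and bases the number of babies on it: "Data from 36 babies would allow such a confidence interval to be calculated to within plus or minus 0.33 of a degree".

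Three other sentences in section 8 bear on the point:

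- A comparison is promised: "Variations from this endpoint will be analysed and compared statistically between the two arms of the study". Section 5 (Study Design) defines the arms as the two orders of incubator use, so each arm contains both incubators.
- A one-degree benchmark for normal fluctuation is given, with the statement "Thus, analysis will explore whether fluctuations for each baby keep within this bound".
- The general approach is qualified: "Although data analysis will be largely descriptive".

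Nowhere does the plan name an estimate or interval for mOm minus standard, a paired or cross-over model, a period term, or how the two intervals are to be read together.

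**The concern.** The question is whether mOm does as well as the standard incubator in the same babies. An interval for each incubator describes each one alone. The pair does not show how large a difference the data allow, and it discards the correlation between a baby's two periods, which is the statistical reason for a cross-over.

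The one-degree benchmark does not fill the gap. It asks whether fluctuation in mOm is normal, not whether it matches the standard incubator.

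The promised comparison between arms does not settle the matter either. Read literally, it compares sequences, and whether that carries any device effect depends on what is compared.

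The risk is that two similar-looking intervals are reported as equal performance when the babies' own paired data show otherwise, or that the difference is never quantified.

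**Working it through.** **Inputs from section 8:** 36 completed datasets; two-sided 95% interval; half-width 0.33 °C; mean fluctuation about 1 °C. No SD and no within-baby correlation (ρ) is given, so both are assumed below.

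**1. The plan's own figure.** Half-width for one incubator = 1.96 × SD / √36. With SD = 1.0 this is 1.96 / 6 = 0.327, which rounds to 0.33 (0.338 with t on 35 df, 2.030 / 6). The stated precision is therefore for a single-incubator mean with an SD of about 1.0 °C.

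**2. Precision of the difference.** Half-width = 2.030 × SD × √(2(1 − ρ)) / 6. For example, SD 1.0 and ρ 0.5 give 2.030 × 1.0 × 1.0 / 6 = 0.338.

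| Assumed SD (°C) | ρ = 0 | ρ = 0.5 | ρ = 0.7 |
|---|---|---|---|
| 1.0 | ±0.48 | ±0.34 | ±0.26 |
| 0.75 | ±0.36 | ±0.25 | ±0.20 |
| 0.5 | ±0.24 | ±0.17 | ±0.13 |

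The stated 0.33 would describe the difference only if SD were about 1.0 and ρ about 0.5.

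**3. What separate intervals can miss.** The plan gives no reading rule, so overlap is used here as an assumed one. Simulation: 36 pairs, bivariate normal, 100,000 trials per setting, assumed true means 1.5 °C (mOm) and 1.0 °C (standard). Entries are for ρ = 0 / 0.5 / 0.7.

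| Assumed SD (°C) | The two intervals overlap | Paired interval lies above 0 (mOm worse) |
|---|---|---|
| 1.0 | 76 / 83 / 88% | 54 / 83 / 96% |
| 0.75 | 51 / 51 / 52% | 79 / 97 / 100% |
| 0.5 | 9 / 3 / 1% | 98 / 100 / 100% |

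At SD 1.0, a higher correlation makes the paired analysis more sensitive and the overlap reading less so. A normal model with mean 1 and SD 1 allows negative fluctuations, so the SD 1.0 row is illustrative.

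**4. The one-degree benchmark.** Take the same 0.5 °C excess at two levels, with SD 1.0. If the true means are 1.5 and 1.0, the mOm interval lies wholly above 1.0 in 83% of trials. If they are 1.0 and 0.5, it does so in 2.5%, which is simply the lower-tail error of a 95% interval. The benchmark responds to mOm's level, not to the difference.

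**5. Comparing arms.** Let δ be the device effect and π the second-period effect.

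- Overall mean of each sequence: baseline + (δ + π)/2 in both, so their contrast is 0 whatever δ is.
- First minus second period: δ − π when mOm comes first, −δ − π when standard comes first. Half the contrast is δ.

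Simulation with δ = 0.5 and π = 0.3 gives 0.00 and 0.50. The sentence on arms allows either reading.

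**6. Period effect (a smaller point).** With 21 babies mOm-first and 15 standard-first, the unadjusted mean difference is δ + π(15 − 21)/36 = δ − π/6. With an assumed π of 0.3 °C the shift is 0.05 °C; adjusting for period removes it. Section 8 says only that "A Microsoft Excel random number generation system will be used to generate random numbers", with no blocking stated. If randomisation is unrestricted, a split at least that uneven among 36 has probability 41%.

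**The case against.** The strongest reply is that the comparison is under-specified rather than absent. Section 8 promises a statistical comparison, says each baby is its own control, calls the analysis largely descriptive, and uses the intervals only to consider the question. This is fair as to intent, and pairing is not ruled out. But a description of the design is not an estimand or a method, and the one measure named for the conclusion is unpaired. An estimated difference with an interval also suits a descriptive study.

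On size, the overlap rule and the 0.5 °C excess are not in the plan, and the largest losses come from SD 1.0. Under the normal model with mean 1, that SD would make about 16% of fluctuations negative. At SD 0.5 the practical loss nearly vanishes. This stands: the overlap figures show one possible misreading and are not a property of the plan. The missing estimate of the difference depends on none of them.

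It also stands that the plan does not fix one fluctuation summary per baby; section 8 speaks of variation, fluctuations and variance. A difference cannot be computed until one is chosen. The plan's own per-incubator intervals share that gap, so it does not count against estimating the difference.

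**Conclusion.** The concern holds and should be fixed before the data are analysed. The stated decision measure cannot quantify the comparative hypothesis, and the precision of the comparison is not declared. That conclusion rests on the text alone and is firm.

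Its practical size is uncertain because the documents give neither SD nor correlation. Over the assumed range, the half-width for the difference at 36 babies runs from ±0.13 to ±0.48 °C. The cost of reading separate intervals ranges from severe at SD 1.0 to slight at SD 0.5.

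**What to change.** In section 8:

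1. Choose one 24-hour fluctuation summary per baby and incubator. Make the primary analysis the within-baby difference (mOm minus standard) in it, with a two-sided 95% interval from a cross-over model with baby, period and incubator type.
2. Reword the sentence on arms so that it compares incubator types within baby.
3. Keep the per-incubator intervals and the one-degree benchmark as description.
4. Restate the precision at 36 babies for the difference, giving its SD and correlation as assumptions.
5. Read the conclusion from the upper limit of that interval, reported as the largest mOm excess compatible with the data. If the sponsor states an acceptable excess in advance, say whether 36 babies suffice; otherwise word the conclusion to the precision achieved.

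**Cost.** Apart from the choice of summary, this is wording and analysis code. Section 6.2 already collects hourly readings in both periods.

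A formal test against an acceptable excess is a separate commitment. With no true difference, one-sided 0.025, SD 1.0 and correlation 0.5, power at 36 babies is 42% for an assumed limit of 0.3 °C (about 90 babies for 80%) and 83% for 0.5 °C. At SD 0.5 and the same correlation it is 94% for 0.3 °C. These limits are illustrations, not proposals.
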